644 more detail below under visit 2). In order to attention-match for interactions with study  
645 staff, participants will attend an asthma education and physical activity training session.  
646 Newsletters with walking tips for AA women and asthma education topics will be sent  
647 twice during the intervention phases to participants in this group. Participants will come  
648 to the Clinical Research Center for data collection at weeks 24 (Visit 7b) and 36 (Visit 9)  
649 described in more detail below.

650  
651 **Asthma and physical activity (PA) education session for all participants (1-6**  
652 **weeks after baseline data collection visit)**

653 The asthma and PA education session will take place at UI Health/UIC or a Chicago  
654 Park District (CPD) location that is in close approximation to where the participants live.  
655 The exact CPD location will be determined with the help of the Chicago Park District  
656 liaison and will take into account safety of the participants and the location of where  
657 participants live. The Chicago Park District will only provide space for these visits and  
658 no Chicago Park District staff are involved in the research as recruiters or to collect  
659 data. Two separate asthma/PA education sessions will take place, one for enhanced  
660 usual care group and one for those randomized into the intervention group.

661  
662 At the asthma/PA education session the following procedures will occur:

663 1. Collection of accelerometers for those that have not already returned it.

- 664 2. Attend a 2 hour group session at the Chicago Park District or at UI  
665 Health/UIC. At the group session, participants will receive didactic asthma  
666 education and information on how to engage in physical activity with their  
667 asthma.  
668 3. Participants will be asked to complete a session evaluation form. (Appendix 9)  
669 4. Participants will be given \$5 cash to assist with travel expenses incurred for  
670 the visit.

671  
672 Key research personnel will send a reminder text, call and/or email (based on patient  
673 preference) up to 3 times the prior week to the group session stating “Asthma and  
674 physical activity session will meet at X time and X place.”  
675

676 An asthma educator, a research assistant(s) and/or [name] will attend the  
677 education session. Each education session will last approximately 2 hours. Patients will  
678 receive light snacks/refreshments at each session.  
679

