714 location that is in close approximation to where the participants live. The exact CPD  
715 location will be determined with the help of the Chicago Park District liaison and will take  
716 into account safety of the participants and the location of where participants live. The  
717 Chicago Park District will only provide space for these visits and no Chicago Park  
718 District staff are involved in the research as recruiters, interventionists, asthma  
719 educators or to collect data.

720  
721 At each group session the following will occur:

- 722 1. Women will attend a 2 hour group session at the Chicago Park District or at  
723 UI Health/UIC. At the group session, participants will continue to receive  
724 asthma education (short videos and/or didactic session), watch a video on  
725 how to get started to walk and what barriers they may face. Participants will  
726 be asked to share their experiences engaging in physical activity with asthma.
- 727 2. Participant will be given an individualized step-goal not to exceed 3000 steps  
728 above their baseline calculated from accelerometer data over the entire  
729 course of the study.
- 730 3. Each participant will be given an ACTION participant manual (1st group  
731 session only).
- 732 4. Participants will be encouraged to walk during the group session for up to 15  
733 minutes. The interventionist and Chicago Park District liaison will identify safe  
734 locations for the women to walk at the group session site. Women will be able  
735 to walk at their own pace and stop at anytime. If the participant does not want  
736 to participate in the walking portion of the group visit they may opt-out by  
737 verbally telling the interventionist that they do not want to participate.
- 738 5. Participants will be asked to complete a session evaluation form. (Appendix  
739 9).
- 740 6. Participants will be given \$5 cash to assist with travel expenses incurred for  
741 each group visit.

742

743 At the last group session in the adoptive phase, the following procedures will occur and  
744 the participant will receive \$35 cash or gift card for this visit only:

745 :

- 746 1. Spirometry performed according to American Thoracic Society guidelines.  
747 Participants will be asked to wear nose clips and to take a deep breath in and  
748 blow their breath out as fast as they can into the spirometer. We will perform  

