749 repeated measurements (3 to 8 times) to ensure accuracy of results.
- 750 2. Weight
- 751 3. Incremental Shuttle Walk Test (ISWT) performed according to American  
752 Thoracic Society guidelines
- 753 4. Accelerometer distribution
- 754 5. Summative evaluation (visit 7 only; Appendix 10)

755

756 If a participant is not able to attend this session, we will contact the patient to scheduled  
757 an in person data collection visit at UI Health/UIC where the above procedures (#1-3)  
758 will be completed.

759

760 During or after Visit 7a is complete, participants will complete REDCap paper surveys (  
761 in person) or will be sent a link (email or text) to complete the following REDCap  
762 surveys electronically:

- 763 1. Physical activity questionnaires
- 764 2. Asthma Safety Measures
- 765 3. Asthma Control Questionnaire (ACQ)
- 766 4. Asthma-related quality of life questionnaire (AQLQ)
- 767 5. Adult Asthma Adherence Questionnaire (AAAQ)
- 768 6. PROMIS measures (Global Health, social roles satisfaction, mood, sleep)
- 769 7. Active Where Questionnaire
- 770 8. Self-efficacy for walking scale
- 771 9. Social support for exercise survey
- 772 10. Outcome expectation scale for exercise
- 773 11. Sleep Apnea Scale of the Sleep Disorders Questionnaire
- 774 12. Pittsburgh Sleep Quality Instrument

775 Key research personnel will send a reminder text, call and/or email (based on patient  
776 preference) up to 3 times the prior week to the group session stating “ACTION Asthma  
777 group will meet at X time and X place.”

778

779 Reminder messages will also be sent via phone, text or email (based on participant  
780 preference) up to 3 times per week to help them attain their weekly step goal (See  
781 Appendix 11 for sample text messaging).

782

783 An interventionist and/or [name] will attend the group sessions. Each group will  
784 last approximately 2 hours and may be audio-recorded to assess for intervention fidelity.  
785 If a participant declines audio-recording the session, then the session will not be  
786 recorded. The PI or co-investigator may then observe a group session intermittently to  
787 assess for intervention fidelity. If the session is recorded, the PI will review portions of  
788 the session. The sessions will be deleted once the pilot is complete. These audio  
789 recordings will not be transcribed. Patients will receive light snacks/refreshments at  
790 each session.

791

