792 If any of the group visits 3-7 are missed, the woman is asked to arrive 15 minutes early  
793 for the next meeting to receive an update. Her report will be emailed/phones/texted to her  
794 depending on her preference.

795

796 If a woman has missed several group visits and we have been unable to contact her, we  
797 will mail her a letter indicating to call us.

798

799 **Visit 7b: 24 week data collection (Enhanced Usual Care only)**

800 At Visit 7b the following procedures will take place at the Clinical Research Center at  
801 UIC:

- 802 1. Spirometry performed according to American Thoracic Society guidelines.  
803 Participants will be asked to wear nose clips and to take a deep breath in and  
804 blow their breath out as fast as they can into the spirometer. We will perform  
805 repeated measurements (3 to 8 times) to ensure accuracy of results.
- 806 2. Weight
- 807 3. Incremental Shuttle Walk Test (ISWT) performed according to American  
808 Thoracic Society guidelines
- 809 4. Accelerometer distribution
- 810 5. Physical activity questionnaires
- 811 6. Asthma Safety Measures
- 812 7. Asthma Control Questionnaire (ACQ)
- 813 8. Asthma-related quality of life questionnaire (AQLQ)
- 814 9. Adult Asthma Adherence Questionnaire (AAAQ)
- 815 10. PROMIS measures (Global Health, social roles satisfaction, mood, sleep)
- 816 11. Active Where Questionnaire
- 817 12. Self-efficacy for walking scale
- 818 13. Social support for exercise survey
- 819 14. Outcome expectation scale for exercise
- 820 15. Sleep Apnea Scale of the Sleep Disorders Questionnaire
- 821 16. Pittsburgh Sleep Quality Instrument

822

823 This visit will last approximately 2 hours and upon completion the participant will receive  
824 \$35 cash or gift card.

825

826 Participants will be given a postage paid envelope and be asked to mail the  
827 accelerometer back to study team after wearing it for 1 week. Reminder  
828 calls/texts/emails will be sent if we have not received the accelerometer within 2 weeks  
829 of completion of visit 7. If needed, a central location for drop-off of the accelerometer  
830 may be arranged with the participant.

831

832 **Maintenance Phase:** During the maintenance phase, participants will continue to  
833 receive reminder text messages to help them attain their weekly step goal no more than  
834 once a week.

835

836 **Visit 8: Post-maintenance booster session and data collection (12 weeks after**  

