837 **Visit 7) Booster session will only be for intervention group.**

838

839 At visit 8 booster session the following procedures will occur:

- 840 1. Attend a 2 hour group session at the Chicago Park District or at UI  
841 Health/UIC. At the group session, participants will review successes attained  
842 and barriers, lapses, and relapses encountered.
- 843 2. Participants will be asked to complete a session evaluation form. (Appendix 9).
- 844 3. Participants will be given \$5 cash to assist with travel expenses incurred for  
845 the group visit.

846

847 An interventionist and/or [name] will attend the group session. The group will last  
848 approximately 2 hours and may be digitally recorded to assess for intervention fidelity. If  
849 a participant declines audio-recording the session, then the session will not be  
850 recorded. The PI or co-investigator may then observe a group session intermittently to  
851 assess for intervention fidelity. If the session is recorded, the PI will review portions of  
852 the session. The session will be deleted once the pilot is complete. These audio  
853 recordings will not be transcribed. Patients will receive light snacks/refreshments at the  
854 session.

855

856 **Post-maintenance data collection (all participants)**

857 The following procedures will take place at the Chicago Park District (intervention  
858 group) or Clinical Research Center at UIC (enhanced usual care):

- 859 1. Spirometry performed according to American Thoracic Society guidelines.  
860 Participants will be asked to wear nose clips and to take a deep breath in and  
861 blow their breath out as fast as they can into the spirometer. We will perform  
862 repeated measurements (3 to 8 times) to ensure accuracy of results.

- 863 2. Weight  
864 3. Incremental Shuttle Walk Test (ISWT) performed according to American  
865 Thoracic Society guidelines  
866 4. Distribution of accelerometer  
867  
868

869 The following questionnaires will be completed by REDCap survey:

- 870 1. Physical activity questionnaires  
871 2. Asthma Safety Measures  
872 3. Asthma Control Questionnaire (ACQ)  
873 4. Asthma-related quality of life questionnaire (AQLQ)  
874 5. Adult Asthma Adherence Questionnaire (AAAQ)  
875 6. PROMIS measures (Global Health, social roles satisfaction, mood, sleep)  
876 7. Active Where Questionnaire  
877 8. Self-efficacy for walking scale  
878 9. Social support for exercise survey  

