## 941 **7.0 Expected Risks/Benefits**

942

943 The research involves minimal risk:

944  
945  
946  
947  
948  
949  
950  
951  
952  
953  
954  
955  
956  
957  
958  
959  
960  
961  
962  
963  
964  
965  
966  
967  
968  
969  
970  
971  
972  
973  
974

1. There is a chance that answering questions about their health may cause participants to become upset or distressed. If this should happen during a focus group or group session, the participant may take a break from the group or leave the group entirely.
2. Questionnaires: given that some questions ask personal information; it is possible that participants will be uncomfortable answering them. Participants will be explained they do not have to answer any question they are uncomfortable with.
3. There is also a chance for loss of privacy and loss of confidentiality in the unlikely event that unauthorized persons should see study data. Many protections will be taken to decrease the chances that this happens.
4. Spirometry (lung function test): risks associated with spirometry are minimal for most people. Because the test involves rapid and forced breathing, some people may experience temporary (lasting up to a few minutes) shortness of breath, lightheadedness and minor chest soreness. In rare cases, the participant may hyperventilate and become dizzy during spirometric testing. Any participant who feels faint should be guided onto the chair with her head down towards the knees, and encouraged to breathe slowly and deeply until she recovers. If the participant fails to recover normal breathing, faints, or reports feeling ill, the research assistant will summon the CRC nurse manager and physician immediately. The physician should always be consulted if there is any question regarding the participant's safety status during the exam.
5. Risk of pulmonary event: subjects will be asked to increase their daily physical activity and will perform up to 15 minutes of walking during the intervention group sessions, so there is the possibility of a pulmonary complication, such as an increase in respiratory symptoms (shortness of breath, cough, wheezing). We will minimize this risk by careful participant selection. Previous studies have shown the safety of increasing physical activity in sub-optimally controlled persistent asthma (Ma J et al. Ann Am Thorac Soc. 2015; 12(1): 1–11.)

975 Participants may have direct personal benefits from participating in the pre-pilot and  

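### Whoever runs spirometry and the shuttle walk at week 24 and post-maintenance is not masked, and arm-specific visits and sites will usually reveal the arm

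*Combined protocol and SAP*

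**What the plan says.** All references are to the combined protocol and SAP.

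- **Education session (Section 6.0, Aim 3).** "Two separate asthma/PA education sessions will take place, one for enhanced" usual care and one for the intervention group. On staffing: "An asthma educator, a research assistant(s) and/or [name] will attend the" session.
- **Intervention group sessions (Section 6.0, Adoption phase).** "An interventionist and/or [name] will attend the group sessions. Each group will" run about two hours. Research assistants are not listed here or for the booster session.
- **Week 24, intervention arm.** "At the last group session in the adoptive phase, the following procedures will occur and" the list that follows includes spirometry and the shuttle walk. Women who miss that session are offered an individual appointment for items 1 to 3 of the list.
- **Week 24, usual care.** The same tests are done under the heading "Visit 7b: 24 week data collection (Enhanced Usual Care only", at the Clinical Research Center.
- **Post-maintenance.** "The following procedures will take place at the Chicago Park District (intervention" group), while usual care is tested at the Clinical Research Center.
- **Who is at the spirometer (Section 7.0, item 4).** If a woman does not recover, "the research assistant will summon the CRC nurse manager and physician immediately". No role is named for the shuttle walk.
- **Masking.** None is described for testers. The nearest text, in Section 8.0, keeps analysts from linking data to identities. That is a confidentiality measure and does not concern testers.

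**The concern.** Spirometry (three to eight efforts per visit) and the shuttle walk both depend on how hard the woman tries, and so on how the tester instructs and encourages her. The women cannot be masked to a group walking programme, so an unaware tester is the main protection left for these two measures. Without one, better coaching in one arm cannot be told apart from a treatment effect.

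Aim 3 (Section 3.0) is meant to estimate efficacy so that a later trial can be powered. If the estimate came from one of these tests and were inflated, the later trial would be too small.

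**Working it through.** **Step 1: could a tester be unaware of the arm under the plan as written?**

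- *Baseline.* Randomization is listed after the tests among the Visit 1 procedures, so baseline measurements are less exposed.
- *Week 24.* One arm is tested at its own group session and the other at a visit reserved for usual care. The occasion itself identifies the arm. The exception is a woman tested at the individual make-up appointment.
- *Post-maintenance.* The site differs by arm, so the location identifies it.
- *Staff overlap.* The education-session staffing and the spirometry safety text together suggest that a research assistant may do both jobs. Nothing says that the same person does.

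The visit structure alone is enough to show that the tester will usually know the arm. Staff overlap is a second, weaker route.

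**Step 2: what size could this have?** The plan states no effect size, SD, alpha, power or bias, so there is no figure to reproduce. What follows is illustration. Assumptions: 80 women split 40 and 40 without dropout; a two-sided 5% test; an arm difference shifted by 0.1 or 0.2 SD.

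SE of the standardized difference = √(2/40) = 0.2236 SD, so the 95% interval half-width is 1.960 × 0.2236 = 0.438 SD.

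False-positive rate with no true effect, P(|Z + shift/SE| > 1.960):

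- shift 0.1: 0.1/0.2236 = 0.447, rate 0.073
- shift 0.2: 0.2/0.2236 = 0.894, rate 0.145

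**Step 3: the next trial.** Assume a true effect of 0.4 SD, seen as 0.5 or 0.6 SD.

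Planned for 90% power, the trial has actual power Φ[(1.960 + 1.282) × true/seen − 1.960]:

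- seen as 0.5: 3.242 × 0.4/0.5 = 2.594; Φ(0.634) = 0.74
- seen as 0.6: 3.242 × 0.4/0.6 = 2.161; Φ(0.201) = 0.58

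Planned for 80% power, n per arm = 2 × (1.960 + 0.842)²/d²:

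| Effect used for planning | n per arm | Actual power at 0.4 SD |
|---|---|---|
| 0.4 (no bias) | 99 | 80% |
| 0.5 | 63 | 61% |
| 0.6 | 44 | 47% |

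**The case against.** **The research assistant's role is inferred.** A reader might conclude that research assistants attend the arm-specific sessions and then run the tests on the same women. The documents do not say so. Section 7.0 puts a research assistant at spirometry in a safety paragraph without assigning the test; attendance at the education session is and/or; no one is named for the shuttle walk. A reader might also infer that visit staff make the allocation. Section 11.0 says only that the REDCap randomization program is used. This part of the objection stands, and the point rests on the visit structure instead.

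**The effect on the next trial is conditional.** No primary efficacy outcome is named. Section 9.0 lists lung function and shuttle walk time only among the data collected, asthma control is the long-term goal in Section 4.0, and accelerometer steps are collected. Neither asthma control nor steps involves coached effort. This stands too.

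**The numbers are assumed.** The shift has no source, the plan specifies no hypothesis test, and 40 per arm ignores dropout. The assumed bias is also smaller than the pilot's SE. All true, although sampling error averages out in a larger trial run the same way and a systematic shift does not.

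**Both tests follow American Thoracic Society guidelines.** The protocol cites these for how the tests are performed. Whether they fix the wording of encouragement cannot be checked from the documents, and the protocol does not use them to say who tests or what that person knows. The procedure tables and survey measures in the appendices are listed but not reproduced.

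**It is only a pilot.** That lowers the stakes, but one stated purpose is an estimate to carry forward.

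**Conclusion.** The plan does not mask the staff who run the week-24 and post-maintenance spirometry and shuttle walk, and does not separate them from session staff. Because testing takes place at arm-specific visits or sites, the tester will usually know the arm. That leaves two effort-dependent outcomes open to expectation or coaching bias.

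The size is unknown. Under an assumed 0.1 to 0.2 SD shift with 40 per arm, a nominal 5% test would reject about 7% to 15% of the time. With a true effect of 0.4 SD, a next trial planned for 90% power would have about 74% to 58%. These figures apply only if a later trial is powered on spirometry or the shuttle walk. Accelerometer steps are much less exposed.

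The documents do not support the stronger statements that research assistants are known to do both jobs, or that the efficacy estimate will in fact be biased. The point is worth correcting, but it does not undermine the pilot's feasibility and acceptability aims.

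**What to change.** Add to Section 6.0, Aim 3, in the general data-collection text, the last adoption-phase session, Visit 7b and the post-maintenance visit:

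> Week-24 and post-maintenance spirometry and shuttle walk tests are run by existing research staff who do not attend or deliver that woman's education or group sessions. The REDCap allocation field is hidden from the test forms. One fixed instruction and encouragement script is used in both arms. Tester ID and whether the tester knew the arm are recorded.

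The and/or staffing of the education session already leaves room for this.

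A separate test appointment for every intervention woman should not be required. It would add a visit for each of them; the existing make-up appointment covers only items 1 to 3 and so omits accelerometer distribution; and the post-maintenance site split would remain. Where the setting reveals the arm, report the tester as unmasked, state this as a limitation, and do not power the next trial on these two outcomes alone when accelerometer steps are available.

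Any analysis that drops unmasked tests should be exploratory at most, because it selects women on a post-randomization event that may differ by arm.

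The cost is a duty rota, REDCap user rights, a script and two form fields. The downsides are less flexible scheduling and masking that will remain incomplete.

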613 Actigraph accelerometer: This will be given to participants to assess their baseline  
614 and post-intervention daily number of steps. Participants will be verbally instructed  
615 to wear it attached to their wrist at all times while awake. The Actigraph  
616 accelerometer (Figure 3) is a research accelerometer (1.8 inches at its largest  
617 dimension, weight 19 grams). This will be returned within 2 weeks of the data  
618 collection visit. The accelerometers can be returned either in person at the asthma  
619 and PA session, in a postage paid envelope or the participant and the research  
620 assistant will find a mutually agreeable place to pick up the accelerometer from the  
621 participant. The participant will not incur any charges if the accelerometer is lost or  
622 stolen. The data from the accelerometers will be downloaded to Actigraph software  
623 (ActiLife 6.13.3) when the accelerometers are returned. Only study ID will be used

624 in the actigraph software. No identifiable information will be maintained in the  
625 Actigraph software.

626  
627 Participants are typically asked to wear the accelerometer for 7 days (does not  
628 have to be consecutive). However, valid baseline measurement of activity can be  
629 obtained with an average of 10 hours per day for 4 days. This is the minimum  
630 amount of accelerometer data required to continue participation in the intervention.  
631 If the participant does not wear the accelerometer for sufficient time to provide valid  
632 baseline measure (ie. an average of 10 hours per day for 4 days), they will be  
633 offered a second opportunity to wear the accelerometer. If the participant declines  
634 or is unable to wear the accelerometer again within 3 weeks of returning the  
635 accelerometer, then the participant will be withdrawn from the study.

636  
637 **Enhanced Usual Care Group (home-based walking program):** The comparison  
638 group will be instructed to achieve a static goal of 10,000 steps per day. The US  
639 Surgeon General recommends accumulating 30 minutes of activity most days of the  
640 week. Assuming that an individual gets 6,000 steps from their other daily activities, 30  
641 minutes of walking can help one achieve a goal of approximately 10,000 steps per day.

642  
643 Participants will be given a Fitbit Charge HR® which will measure their daily steps (see  

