680 For missed sessions, make-up sessions will be offered (in-person or by video).  
681 Continuation in the program will be decided by the PI on a case by case basis.  
682 Participants will be strongly encouraged to make up missed sessions prior to the next  
683 scheduled group session (intervention group) or data collection visit (enhanced usual  
684 care group).  
685

686 Participants will be given the following equipment at the asthma/PA education session:  
687 1) Fitbit® physical activity monitor: Participants will be verbally instructed to wear it on  
688 their wrist at all times while awake. The Fitbit (Figure 4) is a commercially-available  
689 physical activity monitor (0.83 inches wide, weight 0.8 ounces). The wristbands are  
690 adjustable and data from our focus groups revealed that participants would prefer a  
691 wrist-based than a waist-based physical activity monitor. Participants will be asked to  
692 download the fitbit app to their smartphone or tablet and asked to create an account.  
693 Participants will be referred to the Fitbit website for troubleshooting. This will allow for  
694 physical activity data transmission to the Fitbit study database which will not contain any  
695 identifiable information. If a participant is unable to or does not want to download the  
696 fitbit app then they will write their daily steps into a journal which they will bring to each  
697 study visit. Participants will not be responsible for the cost of the Fitbit if it is lost or  
698 stolen.  
699

700 Daily physical activity, heart rate and status of the Fitbit (e.g., battery) will be monitored  
701 in real time using a Fitbit study database. Only physical activity data (i.e., step counts,  
702 time worn using heart rate, minutes active, distance walked) of the participant will be  
703 kept in the Fitbit study database. This is necessary for recording of detailed physical

704 activity data as the pedometers have limited data storage capacity. Only study ID will be  
705 used in the Fitbit study database. No identifiable information will be maintained in the  
706 Fitbit database.

707  
708 **Group sessions (Intervention group only):** Women randomized into the intervention  
709 group will also attend group sessions in 2 phases: Adoption and Maintenance (See  
710 Figure 2).

711  
712 **Adoption phase (5 sessions every 4 weeks)**

713 The group session will take place at UI Health/UIC or a Chicago Park District (CPD)  

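### Aim 3 sets the step-goal ceiling on ActiGraph steps but apparently has women pursue it on a Fitbit, with no planned comparison; separately, the Visit 7a make-up list omits the ActiGraph

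*Combined protocol and SAP*

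**What the plan says.** All references are to the combined protocol and SAP.

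- **Ceiling.** Section 6.0, Aim 3, adoption phase, item 2: "Participant will be given an individualized step-goal not to exceed 3000 steps" "above their baseline calculated from accelerometer data over the entire" course of the study. How the goal is individualized below that ceiling is not described.
- **Baseline device.** The ActiGraph is what the protocol calls the accelerometer. In Aim 3 women are told "to wear it attached to their wrist at all times while awake". On its return: "This will be returned within 2 weeks of the data" collection visit. The education session provides for late returns: "Collection of accelerometers for those that have not already returned it".
- **Device in daily use.** The Fitbit, described as a physical activity monitor, comes next: "Participants will be given the following equipment at the asthma/PA education session". It too is worn on the wrist during all waking hours. Its counts reach the study through the app or a step journal. Later reminders mention a weekly step goal without naming a device.
- **Later ActiGraph wear.** Item 4 of the last adoption session, of Visit 7b and of the post-maintenance collection is distribution of the accelerometer, which is worn for a week. Aim 2 collects the Fitbit at Visit 4; Aim 3 describes no Fitbit return.
- **Missed Visit 7a.** A woman who cannot attend the last adoption session is offered an in-person data collection visit limited to procedures 1 to 3.
- **Analysis.** Section 8.0 lists both Fitbit and accelerometer data. The Aim 3 text in Section 9.0 names neither step counts nor device agreement, and Section 11.0 adds nothing on either.

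**The concern.** A ceiling of 3,000 steps above baseline has a definite meaning only if baseline and goal are counted on the same scale. Here the baseline comes from one device, and the goal appears to be followed on another that is first issued as the first is taken back. If the two count differently, the rise actually asked of a woman is not the rise written in the protocol, and a report that she met her goal cannot be read in the units that define it. Aim 3 is meant to inform a later efficacy trial, so delivered dose and fidelity are worth being able to interpret.

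The make-up rule raises a different issue. It is a question of missing week-24 step data in one arm and does not depend on whether the devices agree.

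**Working it through.** **1. Inputs.** From the documents: the 3,000-step ceiling and 80 women. Assumed: the Fitbit/ActiGraph ratio r (0.90 to 1.10; it may be 1); the baseline B (6,000 is borrowed from the usual-care rationale for 10,000 steps, with 4,000 and 8,000 as a range); the between-woman SD of the ratio (0.10 to 0.20); 70% to 100% of women contributing, so 0.70 × 80 = 56 to 80; and equal allocation, so 28 to 40 per arm. The plan gives no figure of its own to reproduce.

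**2. Rise requested at the ceiling.** If the number B + 3,000 is what a woman aims for on the Fitbit, the ActiGraph-scale rise is (B + 3,000)/r − B.

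| B | r = 0.90 | 0.95 | 1.00 | 1.05 | 1.10 |
|---|---|---|---|---|---|
| 4,000 | 3,778 | 3,368 | 3,000 | 2,667 | 2,364 |
| 6,000 | 4,000 | 3,474 | 3,000 | 2,571 | 2,182 |
| 8,000 | 4,222 | 3,579 | 3,000 | 2,476 | 2,000 |

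At B = 6,000 the rise stays within 250 steps of 3,000 only for r from 9,000/9,250 = 0.973 to 9,000/8,750 = 1.029, a tolerance of about 0.03.

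**3. Alternative goal-setting.** If staff instead add increments to a woman's own Fitbit counts, the ceiling becomes 3,000/r: 3,333 at r = 0.90 and 2,727 at r = 1.10. The discrepancy is then about 300 steps, not 800 to 1,000. The text does not say which applies.

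**4. What existing wear could show.** With continuous Fitbit wear and the ActiGraph re-issued at weeks 24 and 36, overlap is implied. The 95% half-width of the mean ratio is t × SD/√n.

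| Women | t | SD 0.10 | SD 0.20 |
|---|---|---|---|
| 80, pooled | 1.990 | 0.022 (200 steps at 9,000) | 0.045 (401) |
| 56, pooled | 2.004 | 0.027 (241) | 0.054 (482) |
| 40, one arm | 2.023 | 0.032 (288) | 0.064 (576) |
| 28, one arm | 2.052 | 0.039 (349) | 0.078 (698) |

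Pooled estimates come within the 0.03 tolerance only at SD 0.10. No single-arm estimate does.

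**5. The make-up rule.** Two statements in Section 6.0 conflict. The general text on the three data collection visits, which names Visit 7a/b at week 24 and covers all participants, says the ActiGraph is provided at these visits. The make-up rule for Visit 7a stops at item 3, and the accelerometer is item 4. Visit 7b, for usual care, includes the accelerometer and has no shortened make-up. The documents do not say how many women will miss Visit 7a. With 40 in the arm, each one handled by the written list removes 1/40 = 2.5% of the arm's possible week-24 ActiGraph data.

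**The case against.** The strongest reply is that no defect has been shown. The documents give no device ratio, both devices are worn on the wrist, and no sentence states that the goal is tracked on the Fitbit. The participant manual and Appendices 7 and 11, which were not supplied, are where such instructions would naturally sit. The step figures apply only at the ceiling, under an assumed r and B, and shrink if goals are built from Fitbit counts. Goals are given at each session with Fitbit data in view, so one that proves too hard or too easy can be changed. All of this stands and limits the size of the point. It does not supply a statement of the goal's scale, or a comparison, in the text at hand.

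A second reply is that the general rule already provides the ActiGraph at week 24, so the make-up list is only loose drafting. That is possible. But the specific list is what staff would follow at a make-up visit, and the two statements cannot both be right.

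A reader might infer more than the documents support:

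- *The efficacy comparison is biased by the device mismatch.* Steps at baseline and follow-up come from the ActiGraph in both arms, so that comparison stays on one scale.
- *Participants' safety is affected.* The ceiling is not described as a safety limit.
- *The devices must be calibrated before the first goal.* Take four days of dual wear, matching the plan's minimum for a valid baseline ("obtained with an average of 10 hours per day for 4 days"). It would cost up to 80 × 4 = 320 device-days. With an assumed day-to-day SD of 0.05 to 0.10, each woman's ratio would have an SE of 0.05/√4 = 0.025 to 0.10/√4 = 0.05, or 225 to 450 steps at 9,000. If r is near 1, that adds noise to a correct ceiling.
- *Week-24 wear would settle the matter.* The half-widths in the working are too wide in most scenarios to say so.

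**Conclusion.** The point holds, as a minor one and with medium confidence. The ceiling is defined on ActiGraph steps, the goal is by inference pursued on the Fitbit, and the supplied text plans no comparison of the two. Whether this matters in steps is unknown. Under the assumed 10% device difference in either direction and a 6,000-step baseline, the ceiling would mean 2,182 to 4,000 ActiGraph steps if B + 3,000 is the displayed number, and 2,727 to 3,333 if increments are added to Fitbit counts. With no difference it means 3,000. The consequence is confined to intended dose and to the reporting of goal attainment and fidelity.

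The make-up conflict can be read directly from the text and needs no assumption about devices. Followed as written, intervention women who miss the last adoption session lose their week-24 ActiGraph steps, with no matching loss built into usual care. How many women this would be is not known from the documents.

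**What to change.** 1. **Make-up for Visit 7a (Section 6.0, Aim 3).** Change the listed procedures from 1–3 to 1–4, so that the accelerometer is handed out. Cost: one extra week of ActiGraph wear, and its return, for women seen at make-up visits.
2. **Adoption phase, item 2.** State which device scale the goal and ceiling use. If the manual or an appendix already does so, a cross-reference is enough.
3. **Analysis text (Section 9.0, Aim 3).** From the concurrent wear implied at weeks 24 and 36, report the Fitbit/ActiGraph step ratio on matched days, pooled over arms, with a 95% interval. Give the ratio by arm as description only. Use the pooled ratio to express delivered goals and goal attainment in ActiGraph steps. Cost: a small extra analysis, with no new visits or devices.

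Dual-wear calibration before the first goal is not recommended.
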